5.1 Nonclinical Studies

5.2 Clinical Studies

Results of the three completed Phase 1 studies (MT-7117-E01, MT-7117-E02, and MT-7117-E03) conducted with MT-7117 can be found in the Investigator's Brochure.¹¹

Study MT-7117-A01

A Phase 2, randomized, double-blind, placebo-controlled study to assess the efficacy, tolerability, and safety of MT-7117 in subjects with EPP or XLP has been completed. Top-line

data was received on October 25, 2019 from a total of 102 randomized subjects (2 active groups at [REDACTED] or [REDACTED] doses and 1 placebo group with 33, 34, and 35 subjects in each treatment group, respectively). The efficacy results at Week 16 showed an improvement in average daily time (minutes) to first prodromal symptom, which was greater than the placebo for the [REDACTED] (p<0.008) and [REDACTED] (p<0.003) arms, respectively. In the [REDACTED] and [REDACTED] arms, the primary endpoint of time-to-prodrome for MT-7117 versus placebo was > 50 minutes, irrespective of the season of the year. The improvement of time-to-prodrome (primary endpoint) and the duration of sunlight exposure (secondary endpoint) were observed as early as Week 6. Dose-related increase in pigmentation was observed. Treatment-emergent adverse event (TEAE)s leading to discontinuation in the [REDACTED] arm were higher than the placebo (14.3% vs. 0%). TEAEs were observed in System Organ Class (SOC) of nervous system disorders, gastrointestinal disorders, skin and subcutaneous disorders, and general disorders. There was no trend in hepatic adverse event (AE)s, and no trend of clinically significant changes in Liver Function Test (LFT)s were observed. A treatment-emergent serious adverse event (SAE) occurred in one subject (anaphylactic reaction) in the MT-7117 [REDACTED] arm and was unrelated to treatment.

Study MT-7117-A02

A Phase 1 open-label, single-center, parallel-group study to assess the pharmacokinetics, safety, and tolerability of a single dose of MT-7117 in healthy volunteers with normal hepatic function, moderately impaired hepatic function, and mildly impaired hepatic function, is ongoing. Up to 24 subjects are planned to be in this study (8 subjects in each treatment group).

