5 ANALYSIS POPULATIONS

5.1 Randomized (RAND) Population

The randomized (RAND) population includes all randomized subjects.

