5.3 Intent-to-treat (ITT) population

For the DBT data analysis

Intent-to-treat population 1 (ITT1) includes all randomized subjects who received at least 1 dose of study medication with baseline and post-randomization sunlight exposure diary assessment.

For the DBE data analysis

Intent-to-treat population 2 (ITT2) includes all randomized subjects who received at least 1 dose of study medication with baseline and post-randomization sunlight exposure diary assessment during DBE period.

The ITT populations will be used for all efficacy analyses. The subject randomized treatment will be used for efficacy analyses.

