8.2 Efficacy Assessments

All efficacy endpoints will be analysed under primary estimand unless otherwise stated.

All data will be listed.

For DBT data analysis

All efficacy endpoints in Section 2.3.1, 2.3.2, and 2.3.3 will be summarized using descriptive statistics or using the number with percentage in the ITT1 population. All of the statistical model analyses stated in the below sections will be done in the ITT1 only for DBT data analysis only.

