Patients with the first missing value occurring at Week 2 (“W2”) will have their missing Week 2 value replaced by an imputed value from a regression model with [REDACTED]

[REDACTED] and the baseline value (BASE) as explanatory variables. In the next step, patients with their Week 4 (“W4”) value missing will have their missing Week 4 value replaced by an imputed value from a regression model with baseline average daily first to prodromal symptoms and the Week 2 value as explanatory variables. Similar procedure will be used to replace the missing values at week 4, 6, 8 and 10 etc. [REDACTED]

[figure not shown]
[REDACTED] If the imputed value is less than 0 and then the value will be replaced with 0.

The following SAS code for the missing data imputation at Week 26 will be used to make the imputation with the MNAR assumption:

[REDACTED]

- Step 3: The imputed dataset (IMPUTED) generated with the approach described above do contain only non-missing values. MMRM model similar to that described for the primary analysis will thus be run on each of the 100 generated imputed datasets and the differences between the treatment groups at Week 26 will be estimated (and export to data 'ESTIMATES'). Finally, the MIANALYZE procedure in SAS will be applied to combine the results from these analyses to derive an overall estimate of the treatment differences at W26. In addition to the estimates, corresponding 95% confidence intervals and p-values will be calculated.

The following example SAS code will be used:

(3) Non-parametric analysis

Non-parametric analysis will be performed in order to confirm the robustness for the above parametric model. The change from baseline in average daily time (minutes) to first prodromal symptom associated with exposure to sunlight between 1 hour post sunrise and 1 hour pre-sunset at each visit (Weeks 2, 4,..., 24, and 26) from two treatments being compared will enter the corresponding analysis. The point estimates and two-sided 95% confidence intervals for the difference between the treatment groups will be obtained using the Hodges-Lehman estimator corresponding to Wilcoxon's rank sum test. The paired comparison between each MT-7117 arm with placebo will also be performed using this non-parametric analysis method. This non-parametric analysis will be performed with multiple imputation (MI) method in the following steps, assuming missing at random.

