To protect the study from type I error inflation, the lower ordered comparison will be interpreted inferentially only if a statistically significant treatment effect is detected in the higher ordered comparison ($H1 \Rightarrow H2, \dots, H11 \Rightarrow H12$). The following null hypothesis will be sequentially tested via the following order;

H1: There is no treatment difference between MT-7117 [REDACTED] and placebo in change from baseline in average daily time (minutes) to first prodromal symptom associated with exposure to sunlight between 1 hour post sunrise and 1 hour pre-sunset at Week 26.

H2: There is no treatment difference between MT-7117 [REDACTED] and placebo in change from baseline in average daily time (minutes) to first prodromal symptom associated with exposure to sunlight between 1 hour post sunrise and 1 hour pre-sunset at Week 26.

H3: There is no treatment difference between MT-7117 [REDACTED] and placebo in PGIC at Week 26.

H4: There is no treatment difference between MT-7117 [REDACTED] and placebo in PGIC at Week 26.

H5: There is no treatment difference between MT-7117 [REDACTED] and placebo in total number of sunlight-induced pain events defined as prodromal symptoms (burning, tingling, itching, or stinging) with pain rating of 1-10 on the Likert scale during 26-week double-blind treatment period.

H6: There is no treatment difference between MT-7117 [REDACTED] and placebo in total number of sunlight-induced pain events defined as prodromal symptoms (burning, tingling, itching, or stinging) with pain rating of 1-10 on the Likert scale during 26-week double-blind treatment period.

H7: There is no treatment difference between MT-7117 [REDACTED] and placebo in change from baseline for total score in the domain of pain intensity in the PROMIS-57 at Week 26.

H8: There is no treatment difference between MT-7117 [REDACTED] and placebo in change from baseline for total score in the domain of pain intensity in the PROMIS-57 at Week 26.

H9: There is no treatment difference between MT-7117 [REDACTED] and placebo in the percentage of subjects who are responders at Week 26 based on average daily sunlight exposure time to first prodromal symptoms using the within-subject meaningful change of 66 minutes increase.

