8.2.2 Secondary Efficacy Endpoints

The secondary endpoint PGIC at Week 26 will be analyzed using the similar model as specified for the primary analysis (MMRM) replacing the average daily sunlight exposure time to first prodromal symptom baseline covariate with PGIS covariates at baseline visit.

The change from baseline for total score in each domain of physical function and pain intensity in the PROMIS-57 at Week 26 will be analyzed in the same way.

For the total number of sunlight-induced pain events defined as prodromal symptoms with pain rating of 1-10 on the Likert scale during the 26-week double-blind treatment period, the negative binomial regression model with log link will be used. The model will include treatment and the randomization stratification factors as fixed effect. The estimated incidence rate (IR) and its 95% confidence interval for each treatment group, incidence rate ratio (IRR) of each active MT-7117 treatment group versus placebo, 95% confidence interval of the IRR together

with relevant p-values will be reported.

The following example SAS code will be used;

[REDACTED]

The percentage of subjects who are responders based on average daily sunlight exposure time to first prodromal symptom associated with sunlight exposure between 1 hour post sunrise and 1 hour pre-sunset defined by within-subject meaningful change of 66 minutes increase from baseline to Week 26, will be analyzed using logistic regression analysis. The model will include the treatment group and the randomization stratification factors as fixed effect and the baseline average daily sunlight exposure time to first prodromal symptom as covariate. The treatment odds ratio at Week 26 will be estimated using a contrast. The missing data at Week 26 due to no available average daily sunlight exposure time to first prodromal symptom will be addressed as non-responder.

For each secondary efficacy endpoint, a subgroup analysis by region (North America, Europe, Japan, Australia) will be done.

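### ITT1 leaves dosed subjects with no post-randomisation diary out of the H9/H10 responder test and the control-based imputation, whose own rules would cover them (minor; probably very few subjects)

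*SAP*

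**What the plan says.** SAP 5.3 states that ITT1 "includes all randomized subjects who received at least 1 dose of study medication with baseline and post-randomization sunlight exposure diary assessment", and adds that "The ITT populations will be used for all efficacy analyses". SAP 8.2 repeats the restriction for the models: "All of the statistical model analyses stated in the below sections will be done in the ITT1 only for DBT data analysis only". SAP 5.1 also defines an all-randomised set ("The randomized (RAND) population includes all randomized subjects"), but uses it for disposition, deviations, stratification errors and listings, not for any efficacy model.

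Two analyses run on ITT1 have rules for subjects without later data:

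- **Responder test.** H9 and H10 in the fixed sequence (SAP 8.2.1) concern the "percentage of subjects who are responders at Week 26 based on average daily sunlight exposure time to first prodromal symptoms", with a 66-minute threshold. SAP 8.2.2 says: "The missing data at Week 26 due to no available average daily sunlight exposure time to first prodromal symptom will be addressed as non-responder".
- **Control-based imputation.** SAP 8.2.1, sensitivity analysis (2), is specified on the ITT population. Step 1 fills intermittent gaps so that missingness is monotone. Step 2 then begins with "Patients with the first missing value occurring at Week 2", imputed from a regression that includes the baseline value.

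The primary estimand (SAP 2.2.1; Protocol 14.1) defines its population with the same post-randomisation diary condition.

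**The concern.** Having a diary entry after randomisation is something treatment can influence. Someone who records one day and then leaves is in ITT1 and counts as a non-responder at Week 26. Someone who leaves one day sooner, with no record, is dropped from the denominator. The second subject is at least as clear a failure under the SAP 8.2.2 rule, but never reaches it.

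The control-based imputation has a similar gap. It is meant to test the result against unfavourable assumptions about dropout, yet dosed subjects with no post-randomisation diary are removed before Step 2 can assign them control-like values.

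At stake are two confirmatory hypotheses and one sensitivity analysis of the primary endpoint. If exclusions were concentrated in the active arms, the responder rates and the control-based estimate would both come out slightly too favourable to MT-7117.

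**Working it through.** **Planning figures.** SAP 3.3 gives differences of 57 and 52 min, SD 79.3 min and 42 completers per arm. For 57 min, z = 57/(79.3 × √(2/42)) = 3.29, so power is 0.909 (stated 91%). Simulating the fixed sequence with a shared placebo arm gives 0.790 for winning both comparisons (stated 79%). 42/0.8 = 52.5, rounded up to 53; 53 × 3 = 159. The plan's figures reproduce. The point does not depend on them, but 57, 52 and 79.3 are used below. The arm size is 184/3, about 61 (Protocol 8.1).

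**Who is lost.** After Step 1 has filled intermittent gaps, a first missing value at Week 2 means no post-baseline value at all. A subject with diary records but no qualifying day (SAP 7.2.2.3.1 requires non-zero exposure) can still be in ITT1 and use Step 2, so that step is not empty. Those with no post-randomisation record are the ones lost. SAP 5.3 sets no minimum, so one record appears to be enough to stay in.

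**Responder rate.** With x responders among n subjects, leaving out one non-responder changes the rate by x/(n − 1) − x/n = x/[n(n − 1)]. The documents give no responder rates. I assume normal changes with SD 79.3, active equal to placebo + 57 min, and a mean placebo change of 0, 20 or 40 min. This gives responder probabilities of about 20%, 28% and 37% on placebo and 46%, 56% and 65% on active. All k excluded subjects are placed in one active arm and none in placebo. Odds ratios are unadjusted and p-values come from a two-proportion z test.

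| Mean placebo change | k | Active rate, ITT1 → restored | Odds ratio | p |
|---|---|---|---|---|
| 0 | 1 | 27/60 = 45.0% → 27/61 = 44.3% | 3.34 → 3.24 | 0.0029 → 0.0036 |
| 20 | 1 | 33/60 = 55.0% → 33/61 = 54.1% | 3.16 → 3.05 | 0.0024 → 0.0032 |
| 40 | 1 | 39/60 = 65.0% → 39/61 = 63.9% | 3.07 → 2.93 | 0.0027 → 0.0038 |
| 0 | 5 | 25/56 = 44.6% → 25/61 = 41.0% | 3.29 → 2.84 | 0.0037 → 0.0105 |
| 20 | 5 | 31/56 = 55.4% → 31/61 = 50.8% | 3.21 → 2.67 | 0.0025 → 0.0095 |
| 40 | 5 | 37/56 = 66.1% → 37/61 = 60.7% | 3.22 → 2.55 | 0.0022 → 0.0112 |

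Each excluded active subject is worth 0.7 to 1.1 points. The k = 5 rows are a one-sided stress case, not an expectation.

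**Control-based difference.** If k restored active subjects take the placebo mean, the difference d becomes d × (1 − k/61). For k = 1, 57 becomes 56.1 and 52 becomes 51.1, a loss of 57/61 = 0.93 or 52/61 = 0.85 min. This is an upper figure: 57 is a planning difference, and a control-based estimate with dropout already starts lower. If, crudely, the planned 20% dropout all took the placebo mean, the start would be 57 × 0.8 = 45.6 and the loss 45.6/61 = 0.75 min. A restored placebo subject, imputed at the placebo mean, leaves the difference about where it was.

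**The case against.** The strongest reply is that nothing in the plan is broken. The estimand population and the analysis set carry the same condition, and the non-responder rule operates inside ITT1. That stands: this is not an inconsistency between sections. Declaring the restriction in both places does not, however, remove the selection.

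Exclusion is also hard to achieve. Protocol 11.5 requires at least 7 days of outside-exposure data in the 14 days before randomisation, so subjects already use the diary. It is completed daily (Protocol 10.7.1.1), the Week 2 window opens on Day 1 (SAP 7.3, Table 2), and subjects who stop drug are encouraged to stay and complete assessments (Protocol 8.5). Stopping treatment alone does not take anyone out of ITT1. This also stands and is the main reason for the low severity.

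A reader might infer from Phase 2 that the loss is concentrated in the active arms, since discontinuation for adverse events was 14.3% in one active arm against 0% on placebo (Protocol 5.2). The documents do not support that step. The figure is discontinuation of treatment in a 16-week study, not loss before a first diary entry. Applied to 61 subjects it gives about 8.7 over the whole period (0.143 × 61), so k = 5 would need more than half of them to leave without a single record. Exclusions in placebo would push the responder comparison the other way.

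The exclusions will also not be hidden: SAP 8.1.2 summarises and lists the analysis populations on all randomised subjects.

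**Conclusion.** The point holds as a minor one. ITT1 selects on a post-randomisation event, and the subjects it removes would otherwise be non-responders in H9/H10 and would be imputed from Week 2 in the control-based analysis.

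The number affected is not given and is probably near zero. Per subject, in an active arm of about 61, the effect is roughly 1 point on the responder rate and at most about 0.9 min on the control-based difference. These sizes rest on the assumed responder rates and the planning differences. Even five exclusions, all in one active arm, did not carry p past 0.05 in the illustration. H9/H10 are reached only if H1 to H8 all succeed.

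Two stronger readings should be set aside. One is that the plan is biased towards MT-7117: that needs exclusions mainly in the active arms, which is not shown. The other is that the primary result is affected: a subject with no post-baseline value adds nothing to the MMRM likelihood, so that estimate would hardly change.

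**What to change.** - **H9/H10:** analyse all randomised subjects who received at least 1 dose and have a baseline diary value, by randomised arm. Count those with no post-randomisation diary as non-responders. If the data are already unblinded, present this as supplementary.
- **Control-based imputation:** keep the ITT1 run and add a supplementary run on the wider set. Keeping both separates the effect of the population change from that of the missing-data assumption.
- **Reporting:** give the number excluded from ITT1 in each arm. If it is zero, the added runs reproduce the ITT1 results.
- **Leave alone:** the primary MMRM, and the exploratory PGIC responder analysis. PGIC is a separate questionnaire, so a subject without diary data may still have a valid Week 26 rating and should not be coded a non-responder for lack of a diary.

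The cost is SAP wording and one population flag, with no new data. Responder rates may become slightly less favourable.

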5.4 Pharmacokinetic (PK) population

Pharmacokinetic (PK) population for the primary Week 26 analysis includes all randomized subjects who receive at least 1 dose of MT-7117 and who have at least 1 postdose value for plasma concentration at time point to be included in the PK analysis without important protocol deviations which may affect the PK of MT-7117.

PK population for the final analysis includes all randomized subjects who receive at least 1 dose of MT-7117 and who have at least 1 postdose value for plasma concentration at time point to be included in the PK analysis without important protocol deviations which may affect the PK of MT-7117.

6 STATISTICAL CONSIDERATIONS

6.1 Descriptive Statistics

Continuous data will be summarized descriptively using the number in the analysis set (N), the number of observations (n), mean, standard deviation (SD), median, minimum and maximum. Categorical data will be summarized using frequency counts and percentages. The denominator for the percentages will be the total number of subjects in the treatment group and analysis population being presented, unless otherwise specified (e.g. on some occasions, percentages may be calculated out of the total number of subjects with available data at a particular visit and/or time point).

Unless otherwise specified, all data will be summarized by analysis visits and treatment group.

6.2 Statistical Tests

Unless otherwise specified, all formal statistical tests of treatment effects will be done at two-sided significance level of 0.05. Point estimates will be accompanied with two-sided 95% CIs where applicable.

6.3 Stratification registration errors

All patients enrolled into this study were randomized into the IWRS system based on Bracket IRT Randomization List Requirements. [REDACTED]

[REDACTED] in the [REDACTED] system was not consistent with a vendor [REDACTED] report strata and actual baseline TTP strata based on the e-Diary in some

patients. Therefore, it is planned to summarize the status of randomization factor registration error in the section of stratification registration errors and perform the sensitivity analysis for the primary efficacy endpoint to investigate the impact by the errors for study outcome.

7 DATA CONVENTIONS

Prior to the database lock, a blinded data review meeting for Primary Week 26 Analysis and a data review meeting for Final Analysis were conducted. Protocol deviations, protocol defined analysis populations and analysis visits were confirmed during these meetings (Blind Data Review Meeting minutes for Primary Week 26 analysis and Data Review Meeting minutes for Final analysis).

7.1 Treatment Group Definitions and The Corresponding Analyzed Period Data

Two treatment group definitions for DBT data analysis and for DBE data analysis will be used as follows:

For DBT period data analysis

All DBT period data in all Subject type and Follow up period data in Subject type A, B, C and D in Section 4.1 will be analyzed with the below definition.

Treatment Group	Definition
MT-7117 [REDACTED]	Allocated to MT-7117 [REDACTED] group in DBT period
MT-7117 [REDACTED]	Allocated to MT-7117 [REDACTED] group in DBT period

Treatment Group	Definition
Placebo	Allocated to Placebo group in DBT period

For DBE period data analysis

All DBE period data and all Follow up period data in Subject Type A and B in Section 4.1 will be analyzed with the below definition.

Treatment Group	Definition
MT-7117 [REDACTED]	Allocated to MT-7117 [REDACTED] group in DBT period and Enrolled in DBE period.
MT-7117 [REDACTED]	Allocated to MT-7117 [REDACTED] group in DBT period and Enrolled in DBE period.
MT-7117 [REDACTED] (switched from Placebo)	Allocated to Placebo group in DBT period and switched to MT-7117 [REDACTED] group in DBE period.
MT-7117 [REDACTED] (switched from Placebo)	Allocated to Placebo group in DBT period and switched to MT-7117 [REDACTED] group in DBE period.

7.2 Analysis Variable Definitions

7.2.1 Study Subjects

7.2.1.1 Protocol Deviation

Protocol deviations was be documented, reviewed, and determined in the blinded data review meeting for Primary Week 26 Analysis. The major protocol deviations that potentially influence the evaluation of the primary endpoint were selected in this meeting (Blind Data Review Meeting minutes for Primary Week 26 analysis).

7.2.1.2 Demographic and Other Baseline Characteristics

(1) BMI

BMI will be recalculated using the formula below and reported to 1dp.

$$\text{BMI (kg/m}^2\text{)} = \text{weight at screening (kg)} / \{\text{height at screening (m)}\}^2.$$

(2) Disease Duration

Disease Duration (days) = the date of informed consent – the date of diagnosis+ 1.

Disease Duration (years) = Disease Duration (days) / 365.25.

7.2.1.3 Medical History

Medical history will be coded according to the MedDRA version 23.1.

